Appendix H. PUBLICATION POLICY

All unpublished information given to the investigator by the sponsor shall not be published or disclosed to a third party without the prior written consent of the sponsor.

The results of this study may be published or presented at scientific meetings. If this is foreseen, the investigator agrees to submit all manuscripts or abstracts to the sponsor before submission. This allows the sponsor to protect proprietary information and to provide comments.

The sponsor will comply with the requirements for publication of study results:

“Recommendations for the Conduct, Reporting, Editing, and Publication of Scholarly Work in Medical Journals” ([International Committee of Medical Journal Editors \[ICMJE\] Recommendations 2017](#)).

Publication of the results will occur in a timely manner according to applicable regulations. In accordance with standard editorial and ethical practice, the sponsor will generally support publication of multicenter studies only in their entirety and not as individual investigational center data. In this case, a coordinating investigator will be designated by mutual agreement.

Authorship will be determined by mutual agreement and in line with ICMJE authorship requirements:

- substantial contributions to the conception or design of the work; or the acquisition, analysis, or interpretation of data for the work
- drafting the work or revising it critically for important intellectual content
- final approval of the version to be published
- agreement to be accountable for all aspects of the work in ensuring that questions related to the accuracy or integrity of any part of the work are appropriately investigated and resolved

The publications committee established by the sponsor will oversee this process. Additional publications may follow. Policies regarding the publication of the study results are defined in the financial agreement.

No patent applications based on the results of the study may be made by the investigator nor may assistance be given to any third party to make such an application without the written authorization of the sponsor.

App	smart device application
BIPQ	Brief Illness Perception Questionnaire
BMI	body mass index
BMQ	Beliefs about Medicines Questionnaire
CAE	clinical asthma exacerbation
CC	concurrent control
CI	confidence interval
CRF	case report form
CSR	clinical study report
DHP	Digital Health Platform
DS	Digital System
ED	emergency department
ET	early termination
eMDPI	multidose dry powder inhaler with integrated electronic module
GERD	gastroesophageal reflux disease
GINA	Global Initiative for Asthma
HCP	healthcare provider
iHCP	investigational center healthcare provider
IMP	investigational medicinal product
ITT	intent-to-treat
LAMA	long-acting muscarinic antagonist
MAR	missing at random
MedDRA	Medical Dictionary for Regulatory Activities
MI	multiple imputation
MIF	maximal inhalation flow
mITT	modified intent-to-treat
R&D	Research and Development
RTSM	Randomization and Trial Supply Management
SABA	short-acting beta ₂ agonist
SAP	statistical analysis plan
SD	Standard Deviation

Statistical Analysis Plan

Parallel-group, Controlled Study - Asthma
Study ABS-AS-40138

Abbreviation	Term
SE	Standard Error
SOC	system organ class
SOP	standard operating procedure
SUS	System Usability Scale
WHO	World Health Organization

INTRODUCTION

This Statistical Analysis Plan (SAP) describes the planned analysis and reporting for Teva Branded Pharmaceutical Products Research and Development (R&D) study ABS-AS-40138 (**CONN**ected **E**lectronic **I**nhalers **A**sthma **C**ontrol **T**rial 1 (“CONNECT 1”), a 12-Week Treatment, Multicenter, Open-Label, Randomized, Parallel Group Comparison, Feasibility Study to Evaluate the Effectiveness of the Albuterol eMDPI Digital System, to Optimize Outcomes in Patients at Least 13 Years of Age or Older with Asthma), and was written in accordance with GSD_SOP_702 (SAP).

The reader of this SAP is encouraged to read the study protocol for details on the conduct of this study, the operational aspects of clinical assessments, and the timing for completing the participation of a patient in this study.

The SAP is intended to be in agreement with the protocol, especially with regards to the primary and all secondary endpoints and their respective analyses. However, the SAP may contain more details regarding these particular points of interest, or other types of analyses (e.g. other endpoints). When differences exist in descriptions or explanations provided in the study protocol and this SAP, the SAP prevails; the differences will be explained in the Clinical Study Report (CSR).

1. STUDY OBJECTIVES AND ENDPOINTS

1.1. Primary and Secondary Study Objectives and Endpoints

The primary and secondary study objectives and endpoints are:

Objectives	Endpoints
The primary objective of this study is to demonstrate the effectiveness of the Digital System (DS) compared to a concurrent control (CC) group.	The primary endpoint is the proportion of patients for the DS and CC groups achieving meaningful improvement, which is defined as an Asthma Control Test (ACT) score greater than or equal to 20 at the end of the 12-week treatment period or an increase of at least 3 units on the ACT score from baseline at the end of the 12-week treatment period.
The secondary objective (#1) is to describe the asthma management actions by investigational center healthcare providers (iHCPs) for all patients in both groups.	
This secondary endpoint will describe the frequency and types of interventions done to improve asthma control including:
 
 • number of discussions between patient and healthcare provider (HCP) regarding inhaler technique or adherence • number of adjustments of therapy including: 
 ◦ increased or decreased doses of inhaled medication ◦ change to different inhaled medication ◦ additional inhaled medication ◦ addition of a systemic corticosteroid medication for asthma or another controller, including a long-acting muscarinic antagonist (LAMA) or biologics • frequency of intervention to manage comorbid conditions associated with poor asthma control (gastroesophageal reflux disease [GERD], sinusitis, etc.)
The secondary objective (#2) is to evaluate short-acting beta ₂ agonist (SABA) usage and the number of SABA-free days in the DS group.	This secondary endpoint is the change from baseline in the mean weekly SABA usage and the change from baseline in the number of SABA-free days over the 12-week treatment period for the DS group.
The secondary objective (#3) is to assess the usability and acceptability of the DS by patients in the DS group and the investigational center personnel.	This secondary endpoint is the assessment of the DS (eMDPI, App and dashboard) acceptability and usability, utilizing the System Usability Scale (SUS), completed by the patients in the DS group, 18 years of age or older, and the investigational center personnel at the end of the study.

Objectives	Endpoints
The secondary objective (#4) is to assess behavioral correlates of responsiveness to digital health technology among patients for all patients in both groups.	This secondary endpoint is the assessment of patients' beliefs and perceptions about their disease and treatment, utilizing the Beliefs about Medicines Questionnaire (BMQ) and the Brief Illness Perception Questionnaire (BIPQ) to both the DS and CC groups, patients 18 years of age or older, describing their behavioral profile at baseline and at the end of the study.
The secondary objective (#5) is to evaluate the safety of Albuterol eMDPI.	This secondary endpoint is the reporting of adverse events related to Albuterol eMDPI at participating investigational centers. The safety endpoints for this study include the following for all patients in both groups: 
• adverse event data• adverse device effect data

Notes: The Digital System (DS) group will include eligible study population patients who will use the DS (eMDPI, App, DHP [Cloud solution], and dashboard) during the treatment period. The concurrent control (CC) group will include eligible patients who will be treated with their standard of care albuterol-administering rescue inhalers and will not use the DS during the treatment period.

1.2. Exploratory Objectives and Endpoints

Exploratory objectives and endpoints are as follows:

A large rectangular area of the page is completely blacked out with a solid black rectangle, obscuring several lines of text. There are small black vertical marks on the left margin where text was likely present but is now redacted.

2. STUDY DESIGN

2.1. General Design

This is a 12-week treatment, multicenter, open-label, randomized, parallel group comparison feasibility study to evaluate the effectiveness of the Albuterol eMDPI DS, including inhaler, App, Digital Health Platform (DHP, Cloud solution), and dashboard, to optimize outcomes in patients at least 13 years of age or older with asthma.

The study will consist of a screening visit, a 12-week open-label treatment period, and a follow-up telephone call (2 weeks following treatment completion).

Patients with suboptimal asthma control will be enrolled in the study and randomized in a 1:1 ratio to 1 of 2 parallel groups stratified by investigational center: DS group patients utilizing the Albuterol eMDPI DS, including inhaler, App, DHP (Cloud solution), and dashboard, and CC group patients who will be treated with their standard of care albuterol-administering rescue inhalers and will not use the DS during the treatment period. Similar data will be collected regarding outcomes for the CC group: ACT after 12 to 14 weeks, BMQ and BIPQ responses, and the frequency of CAEs.

All patients will have a screening/baseline visit, at which they will be asked if they use a smart device and use different applications on their smart devices. A baseline ACT score for all patients, and BMQ and BIPQ responses for patients 18 years of age or older, will be collected. Once randomized, patients in the DS group will be trained on the use of the Albuterol eMDPI DS (including instructions on how to use both the eMDPI and the App) and, upon demonstrating competency, will receive 2 Albuterol eMDPI devices for use as rescue bronchodilators to replace their rescue treatment during the study. Additional Albuterol eMDPI devices may be supplied during the treatment period, based on patients' needs. Patients in the CC group will be reimbursed or given a voucher to use to purchase their existing rescue medications.

Investigational centers will also receive similar instruction regarding features of the App, as well as features of the associated dashboard, which mirrors the digital information obtained from the eMDPI and App, including frequency and times of SABA rescue use and associated inspiratory flow parameters measured by the eMDPI with each inhalation.

The CC group will be followed according to the clinical judgment of the investigator; the asthma of patients in the CC group will be managed in a manner consistent with the clinical judgment of the investigator and based on asthma management guidelines (eg, GINA). Similar to the management of the CC group, the DS group patients will be followed by the investigational centers with the addition of objective information on Albuterol eMDPI usage being available to both patients and investigational centers through the App and the dashboard, respectively. The iHCPs will check the dashboard at least once a week and use this information, as per their clinical judgment, to modify patients' asthma management. Clinically Driven Assessments for both groups, if necessary, should be arranged per the clinical judgment of the iHCP managing the patient and can be via a telephone call or an on-site visit.

For all patients, at Visit 2 and at each Clinically Driven Assessment, if necessary, the iHCP will record answers to Asthma Management questions regarding what interventions occurred as a

consequence of the Clinically Driven Assessment, including discussions regarding adherence, or inhaler technique, treatment adjustments, or additions of new treatments, including biologic medication usage. Additionally, for patients in the DS group, the iHCP will be asked whether or not the contact with the patient was originated from the iHCP interaction with the dashboard.

At the end of the treatment period (12 weeks), final assessments of the DS and CC group patients will be made, as specified in Table 3 of the study protocol. A follow-up telephone call will be made by the investigational center to all patients, 2 weeks later, and will confirm the DS group patients have returned to previous asthma treatments.

It should also be noted that no specific clinical decisions are being mandated. One secondary objective of this study is to describe how clinicians actually use the information provided by the DS to manage their patients.

Study procedures and assessments with their timing are summarized in Table 3 of the study protocol.

2.2. Randomization and Blinding

This is an open-label study and patients will be randomly assigned to the DS group or CC group in a 1:1 ratio stratified by investigational center, using a Randomization and Trial Supply Management (RTSM) system. Since this is an open-label study, blinding is not applicable.

2.3. Data Monitoring Committee

There will be no Data Monitoring Committee for this study.

[figure not shown]
2.4. Sample Size and Power Considerations

Sample size estimates are based upon the assumption that the absolute differences between the DS and CC group and the associated operational characteristics will be similar to the absolute differences and operational characteristics of the DS and CC groups noted in the sample size rationale for the study design.

The recommended sample size for the study is 150 evaluable patients per group (30 investigational centers with each investigational center enrolling at least 10 patients), 300 patients in total. Accounting for a dropout rate of 10%, this leads to a recommended total number of 330 enrolled patients.

With this sample size and assuming a true absolute difference in proportions (treatment effect as the estimated response rate for the CC group is 60% and for the DS group is 73%) between the groups of at least 13%, the probability that the posterior probability will be at least 95% is 0.77 (power) (analogous to 1-sided p-value < 0.05) ([Merchant et al 2016](#)). Assuming no treatment effect (difference in proportions between the groups is 0%, ie, Type 1 error) then the probability is 0.05 that posterior probability will be at least 95% is 0.05.

It should be noted that both power and Type 1 error are dependent on the absolute difference between the DS and the CC groups as illustrated in Figure 5 of the study protocol by the operational characteristics calculated for the study design.

2.5. Sequence of Planned Analyses

2.5.1. Planned Interim Analyses

There will be no formal interim analysis for this study.

2.5.2. Final Analyses and Reporting

All analyses identified in this SAP will be performed after the end of study as defined in the study protocol.

This SAP and any corresponding amendments will be approved before database lock, in accordance to SOP GBP_RD_702 (SAP).

3. ANALYSIS SETS

3.1. Intent-to-Treat Analysis Set

The intent-to-treat (ITT) analysis set will include all randomized patients. In the ITT analysis set, treatment will be assigned based on the treatment to which patients were randomized, regardless of which treatment they actually received. This analysis population will be used for summarization of patient disposition and demographic and baseline characteristics, as appropriate.

3.2. Modified Intent-to-Treat Analysis Set

The modified intent-to-treat (mITT) analysis set is a subset of the ITT analysis set including only patients who receive at least 1 dose of investigational medicinal product (IMP) (IMP is albuterol eMDPI for the DS group and standard-of-care albuterol-administering rescue medication for the CC group) and at least 1 postbaseline assessment on any of the study endpoints (primary, secondary, or exploratory).

In the mITT analysis set, treatment will be assigned based on the treatment to which patients were randomized, regardless of which treatment they actually received. This analysis will be used for all primary, secondary, and exploratory endpoint analyses.

3.3. Safety Analysis Set

This analysis set will include all patients in the DS group who receive at least 1 dose of IMP and all patients in the CC group. In the safety analysis set, treatment will be assigned based on the treatment patients actually received, regardless of the treatment to which they were randomized, unless otherwise specified. This analysis set will be used for all safety analyses.

4. GENERAL ISSUES FOR DATA ANALYSIS

4.1. General

Descriptive statistics for continuous variables include n, mean, standard deviation (SD), standard error (SE), median, minimum, and maximum. Descriptive statistics for categorical variables include patient counts and percentages, missing category will be displayed as appropriate.

Treatment dates are defined as follows:

- Treatment start date: date of randomization/the screening/baseline visit date.
- Treatment end date: the end of treatment/early termination (ET) visit date. If the end of treatment/ET date is missing then the last contact date will be used.

4.2. Specification of Baseline Values

Baseline is the data observed at that screening/baseline visit, unless otherwise specified.

4.3. Handling Withdrawals and Missing Data

For the primary endpoint, patients who discontinue early due to technology failure, disliking the digital platform, disease worsening, adverse experience or disliking the IMP will be counted as treatment failures. For those who discontinue early not to these reasons, the ACT value assessed at ET visit will be used. Those who discontinue early and do not have an ET visit will be counted as treatment failures.

For the SUS items 1, 3, 5, 7, and 9, if response to 1 item is missing, the missing item will be replaced by the average of the remaining 4 responses. For items 2, 4, 6, 8, and 10, if response to 1 item is missing, the missing item will be replaced by the average of the remaining 4 responses. If response to 2 or more of items 1, 3, 5, 7, and 9 are missing, or 2 or more of items 2, 4, 6, 8, and 10 are missing, the overall SUS score will be set to missing.

For the BMQ subscales, if response to 1 item within a subscale is missing, the missing response will be replaced with the average of the remaining responses within the subscale. If response to 2 or more items within a subscale are missing, the missing responses will not be replaced and the subscale score will be set to missing.

For the BIPQ cognitive subscale, if response to 1 item within the subscale is missing, the missing response will be replaced with the average of the remaining responses within the subscale. If response to 2 or more items within the subscale is missing, the missing responses will not be replaced and the subscale score will be set to missing. For the emotional subscale, if 1 of the responses is missing then the subscale will be set to missing.

4.4. Study Days and Visits

Study days are numbered relative to the treatment start date (ie, ..., -2, -1, 1, 2, ...; with day 1 being the treatment start date and day -1 being the day before the treatment start date).

Weeks are defined in 7-day intervals (days 1 to 7, 8 to 14, ..., 78 to 84). Day 1 is defined as the treatment start date (i.e., date of randomization/Visit 1 visit date).

By-visit (or by-week) summaries will include baseline, and the end of treatment and ET visits.
The ET visit will be summarized as a separate visit.

5. STUDY POPULATION

5.1. General

The ITT analysis set will be used for all study population summaries, unless otherwise specified. Summaries will be presented by treatment group and for all patients.

5.2. Patient Disposition

Patients screened and screened but not randomized (with reason not randomized) will be summarized only for all patients using patient counts. Patients in the ITT analysis set, ITT analysis set who did not attempt to download the App, ITT analysis set who did not use the inhaler, safety analysis set, and mITT analysis set, patients who completed and withdrew from treatment (with reason for withdrawing), and patients who completed and withdrew from the study (with reason for withdrawal) will be summarized using descriptive statistics. The summary will be based on all patients. The denominator for calculating the percentages will be the number of patients in the ITT analysis set.

5.3. Demographics and Baseline Characteristics

The continuous variables of patient age, weight, height, and body mass index (BMI) will be summarized using descriptive statistics. The categorical variables of subject sex, race, and ethnicity will be summarized using descriptive statistics for each category. Missing categories will be presented if necessary.

5.4. Medical History

All medical history will be coded using the Medical Dictionary for Regulatory Activities (MedDRA). The incidence of medical history abnormalities will be summarized using descriptive statistics by system organ class (SOC) and preferred term. Patients are counted only once in each SOC category, and only once in each preferred term category.

5.5. Prior Therapy and Medication

Any prior therapy or medication a patient is taking at the screening/baseline visit will be recorded on the CRF. All prior therapies and medications will be coded using the World Health Organization (WHO) drug dictionary (WHO Drug).

The incidence of prior therapies and medications will be summarized using descriptive statistics by therapeutic class and preferred term. Patients are counted only once in each therapeutic class category, and only once in each preferred term category. Prior therapies and medications will include all medications taken and therapies administered before the treatment start date.

5.6. Study Protocol Deviations

Data from patients with any important protocol deviations during the study will be summarized overall and for each category using descriptive statistics.

6. DATA ANALYSIS

6.1. General

The efficacy of the drug product will not be evaluated in this study. The focus of this study is the engagement of the patient with the Albuterol eMDPI DS.

The mITT analysis sets will be used for all data analyses. Summaries will be presented by treatment group, as randomized.

6.2. Primary Endpoint and Analysis

6.2.1. Definition

The Asthma Control Test (ACT) is a simple, patient-completed tool used for the assessment of overall asthma control. The 5 items included in the ACT assess daytime and nighttime asthma symptoms, use of rescue medication, and impact of asthma on daily functioning. Each item in the ACT is scored on a 5-point scale, with summation of all items providing scores ranging from 5 to 25. The scores span the continuum of poor control of asthma (score of 5) to complete control of asthma (score of 25), with a cutoff score of 19 and below indicating patients with poorly controlled asthma ([Schatz et al 2006](#)).

The primary endpoint is the proportion of patients reaching well-controlled asthma as defined by an ACT score of greater than or equal to 20 or a clinically important improvement in asthma control as defined by an increase of at least 3 units on the ACT score from baseline at the end of the 12-week treatment period (responder analysis of DS versus CC group with responders defined by an ACT score of greater than or equal to 20 or an increase by greater than or equal to 3 units on the ACT score).

6.2.2. Primary Analysis

To analyze the primary endpoint, the following estimand framework will be used:

1. Analysis will be performed on the mITT analysis set.
2. A binary distribution is assumed for the primary endpoint. Patients who discontinue early due to technology failure, disliking the digital platform, disease worsening, adverse experience or disliking the IMP will be counted as treatment failures. For those who discontinue early not due to these reasons, the ACT value assessed at the ET visit will be used.
3. Summary measure: A successful differentiation between the 2 groups will be determined by a Bayesian posterior probability for $\beta_1 > 0$ greater than 0.95 (1-sided). The following statistical methods will be utilized:

Logistic regression model allowing for different response rates at enrolling investigational centers will be used for testing the hypothesis $H_0: \beta_1 = 0$, $H_1: \beta_1 > 0$ in the following model:

$$\ln\left(\frac{p_{ij}}{1-p_{ij}}\right) = \beta_0 + \beta_1 x_i + \beta_2 \text{baseline ACT value} + \text{Center}_j$$

where x_i = treatment group i , p_{ij} = response proportion of treatment group i at Center j , $Center_j$ = random center effect of center j .

Non-informative priors will be assumed for all coefficients. Estimates of mean response rate and corresponding 95% credible intervals for individual proportions, histograms of the posterior response rates, odds ratio with corresponding 95% credible intervals for DS versus CC, and probability of ($\beta_1 > 0$) and probability of (*Odd Ratio* > clinical meaningful value) will be presented.

The SAS code for the primary analysis is as follows:

```
proc mcmc data = x nbi = 1000 nmc = 500000 thin = 20 seed = 159 outpost =
post1 monitor = (beta0-beta2 sigma2 beta1_gt0 pi pi0 pooled or)
statistics=(summary intervals);
parms beta0-beta2 0;
parms sigma2 1;
prior beta0-beta2 ~ normal(mean = 0, var = 1000);
prior sigma2 ~ igamma(shape = 0.001, scale = 0.001);
random b0 ~ normal(mean = 0, var = sigma2) subject = CENTER;
eta = beta0 + b0 + beta1*trt + beta2*y0;
pi = logistic(eta);
pi0 = logistic(beta0 + b0 + beta2*y0);
model count ~ binomial(n = total, p = pi);
array or[<# of sites>];
or[1] = exp(b0 + beta1);
pooled = exp(beta1);
beta1_gt0 = beta1 > 0;
run;
```

where count = number of responders and total = number of patients.

To include study center into the model, the study centers may be pooled according to the number of patients enrolled at each center by keeping the largest centers intact and pooling the remainder of the larger sites with smaller sites to form pooled sites. A final plan for pooling will be made and documented in Statistical Data Review meeting minutes prior to database lock. In addition, summary statistics for the ACT score will be presented at baseline, and the end of treatment and ET visits. ACT score values and changes from baseline to each visit will be summarized using descriptive statistics.

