9.5.4. Planned Method of Analysis

9.5.4.1. Primary Analysis

To analyze the primary variable, the following estimand framework will be used:

1. 1. Analysis will be performed on the mITT set.
2. A binary distribution is assumed for the primary endpoint. Patients who discontinue early due to technology failure, disliking the digital platform, disease worsening, adverse experience or disliking the IMP will be counted as treatment failures. For those who discontinue early not due to these reasons, the ACT value assessed at the ET visit will be used.
3. Summary measure: A successful differentiation between the 2 groups will be determined by a Bayesian posterior probability for $\beta_1 > 0$ greater than 0.95 (1-sided). The following statistical methods will be utilized:

Logistic regression model allowing for different response rates at enrolling investigational centers will be used for testing the hypothesis $H_0: \beta_1 = 0$, $H_1: \beta_1 > 0$ in the following model:

$$\ln \frac{p_{ij}}{1 - p_{ij}} = \delta_j + \beta_0 \text{baseline ACT value} + \beta_1 x_{ij}$$

where i = treatment group, j = investigational center, x_{ij} = treatment group i for investigational center j , p_{ij} = response proportion of treatment group i in investigational center j .

Non-informative priors will be assumed for all coefficients.

Estimates of odds ratio and individual proportions with corresponding credible intervals will be presented.

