6.3.1.2. Analysis

Frequency and types of interventions during the 12-week treatment period will be summarized as count data using descriptive statistics. In addition, similar Bayesian analysis specified for primary endpoint will be performed for those variables separately using Poisson regression. The suggested SAS code for the analyses is as follows:

```
proc mcmc data = x nbi = 1000 nmc = 100000 thin = 20 seed = 159 outpost = post2
  monitor = (beta0-beta3 sigma2 beta1_gt0 lambda lambda0 pooled) statistics=(summary
  intervals);
  parms beta0-beta3 0;
  parms sigma2 1;
  prior beta0-beta3 ~ normal(mean = 0, var = 1000);
  prior sigma2 ~ igamma(shape = 0.001, scale = 0.001);
  random b0 ~ normal(mean = 0, var = sigma2) subject = CENTER;
  eta = beta0 + b0 + beta1*trt + beta2*logt + beta3*y0;
  lambda = exp(eta);
  lambda0 = exp(beta0 + b0 + beta2*logt + beta3*y0);
  model hosp ~ poisson(lambda);
  array lmda[<# of sites>];
  lmda[CENTER] = exp(b0 + beta1 + beta2*logt + beta3*y0);
  pooled = exp(beta1);
  beta1_gt0 = beta1 < 0;
run;
```

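### Some outputs printed by the SAP's Bayesian programs are not what their names or the text say; the success probability and overall odds ratio are right if DS is coded 1

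*SAP*

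**What the plan says.** SAP 6.2.2 fits a Bayesian logistic model with treatment, baseline ACT and a random center intercept. Success means a posterior probability above 0.95 that β1 is positive. The text promises "Estimates of mean response rate and corresponding 95% credible intervals for individual proportions", histograms of the response rates, the DS-versus-CC odds ratio with its credible interval, and Pr(β1 > 0). Protocol 9.5.4.1 makes a shorter promise: "Estimates of odds ratio and individual proportions with corresponding credible intervals will be presented".

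The listing that follows is presented as the code for the primary analysis. Its output list is "monitor = (beta0-beta2 sigma2 beta1_gt0 pi pi0 pooled or". It declares "array or[<# of sites>" and assigns one element, "or[1] = exp(b0 + beta1". The control-side probability is "pi0 = logistic(beta0 + b0 + beta2*y0". The response is binomial, with responders counted out of a number of patients, and the posterior draws are saved to a dataset.

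SAP 6.3.1.2 describes an analysis similar to the primary one, using Poisson regression, and gives suggested code. Its output list is "monitor = (beta0-beta3 sigma2 beta1_gt0 lambda lambda0 pooled", and the direction indicator is "beta1_gt0 = beta1 < 0".

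The SAP Introduction says that the SAP prevails over the protocol where they differ. SAP 2.5.2 says that the SAP is approved before database lock.

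**The concern.** A programmer who completes the primary listing as written would print two quantities that look like odds ratios, with different values and intervals, and only one compares DS with CC. No printed response rate would correspond to the planning values of 60% and 73%. In secondary #1, a variable with the same name as the primary success indicator holds the opposite tail. For counts of discussions or therapy adjustments neither sign is plainly the favorable one, so a reader has only the label to go by.

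What is at stake is the accuracy of reported estimates and labels. If they are left open, someone will have to choose definitions after seeing open-label data.

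**Working it through.** **The plan's own figure.** SAP 2.4 gives 150 per group, 60% versus 73%, one-sided 0.05 and power 0.77. The average rate is 0.665, so the null SE is √(2 × 0.665 × 0.335 / 150) = 0.0545. The alternative SE is √((0.60 × 0.40 + 0.73 × 0.27) / 150) = 0.0540. Power is Φ[(0.13 − 1.645 × 0.0545) / 0.0540] = 0.773, which reproduces 0.77. Nothing below enters this calculation.

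**Treatment coding.** `pi0` is `pi` with the treatment term removed. It is a control probability only if trt = 0 for CC, hence trt = 1 for DS. On that coding the primary `beta1_gt0` averages to Pr(β1 > 0) and `pooled` = exp(β1) is DS versus CC. The SAP does not state the coding.

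**The `or` array.** For center j at baseline ACT y0:

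- DS: logit p = β0 + b_j + β1 + β2·y0
- CC: logit p = β0 + b_j + β2·y0
- difference = β1

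The odds ratio is therefore exp(β1) in every center. By contrast exp(b_j + β1) = exp(b_j) × exp(β1), which sets DS in center j against CC in a center whose intercept is zero. Only element 1 of a per-site array is assigned, and nothing ties it to a particular center. The parallel array in SAP 6.3.1.2 is indexed by center.

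**Illustrative size.** The documents give no between-center SD, so it has to be assumed. The model was fitted with the SAP's priors to 100 simulated trials per setting, each with 30 centers of 10 patients. Baseline ACT was assumed roughly normal(14, 3), restricted to 5–18. Marginal rates were 60% and 73%, which needs exp(β1) of 1.84 to 2.07 given center and baseline. The log shift is for a center truly 1 SD from average, after shrinkage. The factor is exp(∓shift), which multiplies whatever exp(β1) is.

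| Assumed center SD / baseline slope | Log shift | Factor on exp(β1), below / above | Log-scale interval width, `or` ÷ `pooled` |
|---|---|---|---|
| 0.1 / −0.2 | 0.007 | 0.99 / 1.01 | 1.4 |
| 0.3 / −0.1 | 0.052 | 0.95 / 1.05 | 1.5 |
| 0.5 / −0.2 | 0.135 | 0.87 / 1.14 | 1.8 |
| 0.8 / −0.3 | 0.383 | 0.68 / 1.47 | 2.2 |

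With exp(β1) = 2.07, the last row would print about 2.07 × 0.68 = 1.41 or 2.07 × 1.47 = 3.04. These factors should not be applied to the marginal odds ratio (0.73/0.27)/(0.60/0.40) = 1.80, because the shifts are conditional on center and baseline.

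A separate single simulated trial (center SD 0.5, baseline slope −0.05) gave `pooled` a median of 3.49 (95% interval 2.06 to 6.12). Across centers, the median of exp(b_j + β1) ran from 1.12 (0.31 to 3.57) to 6.69 (2.09 to 30.22). The lowest center's interval includes 1 although that of `pooled` does not.

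**`pi` and `pi0`.** Each is one symbol that contains one record's b0 and y0, and on a CC record the two are equal. Nothing averages them over a group or indexes them by center and group. In the single simulated trial, with one record per patient, rates averaged over all patients were 0.78 (DS) and 0.54 (CC). Record-level posterior means ran from 0.54 to 0.89 for `pi` on DS records and from 0.26 to 0.71 for `pi0`. The spread depends on what a record is. At center SD 0.5 and slope −0.2, the middle 95% of `pi0` was 0.35–0.84 with patient records, and by approximation 0.44–0.75 with group-by-center cells of five. Neither is a group rate.

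**Secondary #1.** The variable is the indicator of β1 < 0, so its posterior mean is 1 − Pr(β1 > 0). For Pr(β1 > 0) = 0.97 it prints 1 − 0.97 = 0.03. `lambda` and `lambda0` are tied to one record's center, log time and baseline, as `pi` and `pi0` are. The `lmda` array omits β0, but it is not monitored.

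**The case against.** The best defense is that every promised decision quantity is delivered. `pooled` is the DS-versus-CC odds ratio, the primary `beta1_gt0` is the success probability, and no sentence in the SAP calls `or` the DS-versus-CC ratio. The listing is a template: its array size is a placeholder, so it cannot run unedited. Draws are saved, and the promised histograms and the probability of exceeding a clinically meaningful odds ratio are not in the listing either, so further programming is clearly expected. The response is a count out of a total, and the text defines the proportion by group and center. A record may therefore be a group-by-center cell, and `pi` on that record may be the promised individual proportion. Secondary #1 code is only suggested, that endpoint has no success threshold, and SAP 7 says there is no hypothesis testing.

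Much of this stands. It limits the point to reporting, and it means that record-level ranges based on one-patient records cannot be taken as what the program will print. It does not rescue `or`: filling the whole array would give one value per site, none of them DS versus CC within that site. Nor can they be read as center-specific treatment effects, because the model has none. Under the cell reading, a single monitored symbol still does not print the full set of cells, and the SAP does not say which baseline ACT value a cell carries. Calling the secondary code suggested does not reconcile a name with the opposite inequality.

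**Conclusion.** The point holds as a defect of reported outputs and labels, of minor to should-fix weight. The algebra for `or` and the sign in secondary #1 need no assumption beyond the SAP's own model and code. The numerical sizes are illustrative: they rest on assumed center SDs, baseline slopes and baseline ACT distributions. With little variation between centers the shift in `or` is trivial, although its interval was still 1.4 times as wide in the smallest setting tried.

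A reader might infer more, and the documents do not support it:

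- That the success decision is miscoded. It is correct if trt = 1 for DS and 0 for CC, and power and sample size are untouched.
- That the trial will lack a valid odds ratio or cannot report group rates. `pooled` is valid, and the saved draws allow both group rates and center-by-group rates.
- That secondary #1 reports the wrong direction. The SAP does not say which direction is intended; only the name and the code conflict.

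**What to change.** - Both programs: state that trt = 1 for DS and 0 for CC.
- Primary: delete the `or` array and its entry in the output list, and report `pooled` as the DS-versus-CC odds ratio. Leave `pooled` and the primary `beta1_gt0` unchanged.
- Primary: compute the promised response rates in each posterior draw and say which they are. They could be group rates, for example predictions averaged over mITT patients with trt set to 1 and then to 0. They could instead be center-by-group rates at a stated baseline ACT. Take the credible intervals and histograms from those draws.
- Secondary #1: make the variable name and the inequality agree, and state the direction reported. Treat `lambda` and `lambda0` like the response rates, and delete the unmonitored `lmda` array.

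The cost is a few lines of SAP code and a sentence or two of definition before database lock. Data collection, sample size, priors and the success rule do not change.
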